4.2. SCIENTIFIC RATIONALE FOR STUDY DESIGN

We postulate that risankizumab, an anti-IL-23 biologic used to treat moderate to severe plaque psoriasis, may lead to high levels of prolonged skin clearance due to an effect on resident memory T (Trm) cells. Here, we describe a pilot study that explores whether higher induction doses of risankizumab (4X and 2X standard induction doses) can more effectively target Trm cells within psoriatic lesions, and whether more profound knock-down of Trm cells is associated with higher levels of complete clearance (i.e., PASI 100) and for longer periods of time.

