1. PROTOCOL SUMMARY

1.1. SYNOPSIS

Title: “Decreasing resident memory T cells while increasing clinical durability: higher induction doses of risankizumab for moderate-to-severe plaque psoriasis (KNOCKOUT)”

Study Description: This is a pilot study that explores whether higher induction doses of risankizumab (2x and 4x standard induction doses) can more effectively target resident memory (Trm) cells within psoriatic lesions, and whether more profound knock-down of Trm is associated with higher levels of complete clearance (i.e., PASI 100) and for longer periods of time.

Objectives: **Primary Objective:** to determine whether the reduction in the number and/or effector function of epidermal CD8+CD103+ Trm cells at Week 52 (compared to baseline numbers) in psoriasis patients treated with 4X standard induction doses of risankizumab (600 mg at Weeks 0, 4, and 16) is greater when compared to psoriasis patients treated with 2X standard induction doses of risankizumab (300 mg at Weeks 0, 4, and 16).

Secondary Objectives:

- 1) to compare the percentage of patients with PASI 100 (complete clearance) at Weeks 28, 40, 52 and 100 in patients receiving 4X standard induction doses of risankizumab vs. those receiving 2X standard induction doses of risankizumab and
- 2) to compare safety events over 100 weeks in patients receiving 4X standard induction doses of risankizumab vs. those receiving 2X standard induction doses of risankizumab

[figure not shown]

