3. OBJECTIVES AND ENDPOINTS

OBJECTIVES	ENDPOINTS	JUSTIFICATION FOR ENDPOINTS

Primary Objective: to determine whether the reduction in the number and/or effector function of epidermal CD8+CD103+ Trm cells at Week 52 (compared to baseline numbers) in psoriasis patients treated with 4X standard induction doses of risankizumab (600 mg at Weeks 0, 4, and 16) is greater when compared to psoriasis patients treated with 2X standard induction doses of risankizumab (300 mg at Weeks 0, 4, and 16).
	
Primary Endpoint: change from baseline in number and/or effector function of epidermal CD8+CD103+ Trm cells at Week 52 in psoriasis patients treated with 4X standard induction doses of risankizumab (600 mg at Weeks 0, 4, and 16) or 2X standard induction doses of risankizumab (300 mg at Weeks 0, 4, and 16).
	
Trm cells are the primary cells within psoriatic lesions (and healed skin) that are responsible for psoriasis recurrences after skin lesions have cleared. Targeting these cells, as proposed here, may lead to prolonged remission of psoriasis.

Secondary Objectives:
 
 1) to compare the percentage of patients with PASI 100 (complete clearance) at Weeks 28, 40, 52, and 100 in patients receiving 4X standard induction doses of risankizumab vs. those receiving 2X standard induction doses of risankizumab and 2) to compare safety events over 100 weeks in patients receiving 4X standard induction doses of risankizumab vs. those receiving 2X standard induction doses of risankizumab. 	
Secondary Endpoints:
 
 1) PASI 100 (complete clearance) response at Weeks 28, 40, 52, and 100 in patients receiving 4X standard induction doses of risankizumab or those receiving 2X standard induction doses of risankizumab and 2) safety events over 100 weeks in patients receiving 4X standard induction doses of risankizumab or those receiving 2X standard induction doses of risankizumab. 	
These are standard measures of efficacy and safety for psoriasis studies.

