4. STUDY DESIGN

4.1. OVERALL DESIGN

The overall hypothesis for this study is to determine whether high-dose risankizumab, an anti-IL-23 blocker approved for plaque psoriasis, can target Trm cells with psoriatic lesions, and whether a more marked reduction of Trm cells correlates with high levels of efficacy and longer periods of disease remission.

In summary, this is single-center, randomized, interventional, Phase 2 study (KNOCKOUT) consisting of a 52-week double-blind period followed by a 48-week unblinded extension comparing tissue and clinical effects of 4X standard induction doses of risankizumab vs. 2X standard induction doses of risankizumab in patients with moderate-severe plaque psoriasis.

Twenty patients with moderate to severe plaque psoriasis will be randomized in a 1:1 manner to receive either risankizumab 600 mg (4X dosing) or 300 mg (2X dosing), SC, at Weeks 0, 4, and 16. All patients will receive four SC injections at Weeks 0, 4, and 16 (into right arm, left arm, right thigh, left thigh) by an unblinded pharmacist. For patients randomized into the highest induction dose arm, each shot will contain 150 mg of risankizumab; for patients randomized into the 2X induction dose arm, two shots will contain 150 mg of risankizumab each and 2 shots will contain placebo (sterile saline).

Skin biopsies of lesional and/or non-lesional skin will be obtained at Week 0, and an additional skin biopsy of lesional skin will be obtained at Week 52. These samples will be processed for immunohistochemical staining and RNA seq analysis. Psoriasis severity clinical assessments (PASI, sPGA, BSA) and safety assessments (vital signs, history) will be assessed at screening and Weeks 0, 2, 4, 8, 12, 16, 22, 28, 34, 40, 46, 52, 58, 64, 70, 76, 82, 88, 94, and 100 (to assess secondary and additional endpoints). Routine labs will be performed at Screening and at Weeks 4, 8, 22, and 52.

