8. STUDY ASSESSMENTS AND PROCEDURES

8.1. EFFICACY ASSESSMENTS

Clinical Assessments

All assessments will be performed at Oregon Medical Research Center, P.C. At screening, Week 0, Week 2, Week 4, and every visit thereafter until Week 100, the following will be done:

1. Physical examination (*complete exam at screening, baseline, Week 4, Week 16, and Week 52; targeted exam at every other visit per Investigator discretion)
2. Psoriasis Area and Severity (PASI)
3. Body Surface Area (BSA)
4. Static Physician's Global Assessment (sPGA)
5. DLQI (*at Weeks 0, 28, and 52 only)
6. Vital signs (temperature, blood pressure, heart rate, respiratory rate, and weight)
7. Past medical history, including past systemic treatments for psoriasis (*at screening visit only)
8. Columbia Suicide Severity Rating Scale (*at screening visit only)
9. Interim health history to assess for possible adverse events (*at all visits following the baseline visit)

Laboratory Assessments

At screening, Weeks 4, 8, 22, and 52, the following will be collected at Oregon Medical Research Center, P.C. and sent to a local laboratory:

1. Complete blood count (CBC) w/differential
2. Comprehensive metabolic panel
3. Urinalysis
4. Urine pregnancy test (*performed on-site only for women of child-bearing potential, at each visit up to Week 52, except Week 2)

At screening only, the following will be collected at Oregon Medical Research Center, P.C. and sent to a local laboratory:

1. HIV antibody
2. Hepatitis B panel
3. Hepatitis C antibody
4. Quantiferon Gold

At Weeks 0 and 52, the following will be collected at Oregon Medical Research Center, P.C. and shipped to the laboratory of [name] at the University of Michigan:

1. One 6 mm skin biopsy of lesional skin (at Weeks 0 and 52) and one 6 mm skin biopsy of peri-lesional skin (at Week 0); both will be bisected and processed as follows:

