9.7. METHODS FOR ANALYSIS OF SECONDARY OUTCOMES

For binary endpoints, after handling of intercurrent events in Section 9.4, the proportion will be summarized with percentage, 95% confidence interval, and compared between the two treatment arms with Fisher's exact test.

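### Durability of clearance is a stated aim and PASI is scored every 6 weeks to Week 100, but no endpoint or analysis measures how long clearance lasts

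*Combined protocol and SAP*

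**What the plan says.** Durability appears in several places. The title in the Synopsis (Section 1.1) begins "Decreasing resident memory T cells while increasing clinical durability". Section 4.1 gives the overall hypothesis as "whether a more marked reduction of Trm cells correlates with high levels of efficacy and longer periods of disease remission". Section 4.2 speaks of "higher levels of complete clearance (i.e., PASI 100) and for longer periods of time", and the endpoint justification in Section 3 says "Targeting these cells, as proposed here, may lead to prolonged remission of psoriasis".

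The data to measure it are scheduled. Section 4.1 puts PASI at screening and at "Weeks 0, 2, 4, 8, 12, 16, 22, 28, 34, 40, 46, 52, 58, 64, 70, 76, 82, 88, 94, and 100", and Section 8.1 confirms it at "every visit thereafter until Week 100". The last dose is at Week 16, and Section 4.4 gives 84 weeks of observation after it. The schema (Section 1.2) says the visits after Week 52 serve safety and maintenance of efficacy.

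The endpoints are different in kind. The primary endpoint (Section 3) is a tissue measure, "change from baseline in number and/or effector function of epidermal CD8+CD103+ Trm cells at Week 52". The secondary efficacy endpoint is PASI 100 at Weeks 28, 40, 52 and 100. The additional endpoints include PASI 75, 90 and 100 response, sPGA 0/1 and change in PASI and BSA, at timepoints that are not named. Section 9.7 summarises binary endpoints by percentage and 95% CI, "compared between the two treatment arms with Fisher's exact test". Nothing defines time to loss of clearance, duration of remission or time spent clear.

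**The concern.** A proportion clear at a given week does not say how long clearance lasted. A patient who relapses at Week 58 and one who relapses at Week 94 are both non-responders at Week 100. A patient who loses and regains clearance between two landmarks looks continuously clear. A patient clear through Week 94 who then leaves for a reason unrelated to efficacy adds nothing to the Week 100 proportion under the as-observed rule in Section 9.9, although 66 weeks of clearance after Week 28 were recorded.

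At stake is whether the trial reports any estimate for one of its stated aims. The overall hypothesis also links Trm reduction to length of remission, and without a duration variable there is nothing to relate the Trm change to. The primary Trm endpoint itself is not affected.

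**Working it through.** The plan states no power or effect size, so it has no figure to reproduce.

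**1. Visit count (Section 4.1 schedule).** There are 19 post-baseline PASI visits. After the last dose at Week 16 there are 14, and from Week 28 onward 13 (28, 34, …, 100). The named landmarks use 4 of those 13. Strictly between Weeks 52 and 100 lie 58, 64, 70, 76, 82, 88 and 94: seven visits, none a named timepoint. The landmarks place a relapse in that span within 100 − 52 = 48 weeks; the visits place it within 6.

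**2. Assumptions for size (not from the documents).** 10 per arm; exponential time to loss after Week 28 with medians 24 and 72 weeks; 100% or 80% clear at Week 28 in both arms; no dropout; two-sided 0.05.

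**3. Expected landmark proportions.** P(clear at week w) = c × 2^(−(w−28)/median), with c the proportion clear at Week 28. For c = 1:
- Week 52: 2^(−24/24) = 50% vs 2^(−24/72) = 79%
- Week 100: 2^(−72/24) = 12.5% vs 2^(−72/72) = 50%

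Exact Fisher power, summed over all outcomes at 10 per arm, is about 12% at Week 52 and 24% at Week 100. With c = 0.8 it is 7% and 15%.

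**4. Time to loss against the four landmarks together.** Simulated trials used the 6-weekly visits and kept all 20 patients, with those not clear at Week 28 counted as events at the origin (3,000 replicates).

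| Clear at Week 28 | Log-rank | Any of four Fisher tests, p < 0.05 |
|---|---|---|
| 100% | 50–53% | 31–32% |
| 80% | 30–32% | 21% |

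The lower log-rank figure is the permutation version and the upper is the asymptotic one. With equal medians of 24 weeks the asymptotic log-rank rejects about 6%, the permutation version about 5% and any of the four landmarks about 3%. Part of the gap is therefore Fisher's conservatism.

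Over a wider set (2X-arm median 12, 24 or 36 weeks; hazard ratio 0.5 to 0.25; 70% clear in both arms, or 60% vs 80%), log-rank power runs from about 13% to 65%, and any of four from about 7% to 41%.

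**5. Events available.** With medians 24 and 72 and all clear at Week 28, expected events are 10 × (1 − 0.125) + 10 × (1 − 0.5) = 13.75. The Schoenfeld formula, 4(1.96 + 0.84)²/(ln HR)², asks for about 26 events for 80% power at HR 0.33.

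**6. What a duration estimate would look like.** The restricted mean time clear over the 72 weeks from Week 28 is (m/ln 2)(1 − 2^(−72/m)). For m = 24 it is 34.6 × 0.875 = 30.3 weeks; for m = 72 it is 103.9 × 0.5 = 51.9 weeks; the difference is 21.6 weeks. The variance of time clear truncated at 72 weeks is (2/λ²)[1 − e^(−72λ)(1 + 72λ)] minus the squared mean, with λ = ln 2/m. That is 557 and 613. The standard error is √((557 + 613)/10) = 10.8 weeks, so the 95% CI is about 21.6 ± 21.2 weeks. This ignores the 6-week grid.

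**The case against.** The strongest reply is that Sections 9.1, 9.2 and 9.11 call the study exploratory, descriptive, sized by feasibility and not powered, and the primary endpoint is Trm change. Low power for durability is then the declared position, not a fault. That stands, and it limits the point to estimation. It does not answer it: hypothesis-generating work needs estimates, and landmark proportions do not estimate duration.

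A reader might infer that the plan looks at PASI 100 only four times and throws away most of the information. The documents do not support this. The additional endpoints include PASI 75, 90 and 100 response at further timepoints, and Section 9.7 is worded for binary endpoints generally. Nine of 13 visits from Week 28 are not named, but in most of the scenarios above the four landmarks together keep roughly half to 70% of the log-rank's power. What remains true is that all these summaries are cross-sectional.

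Section 9.1 leaves full details to an SAP, and no separate SAP is in the text supplied. A Kaplan-Meier display could appear there, but it would be an analysis of an endpoint that Section 3 does not list.

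Exponential loss gives proportional hazards, which favours the log-rank, and the threefold ratio of medians is an assumption. Finally, Section 6.3 unblinds patients, staff and investigators at Week 52, so later relapse timing is open-label. That also applies to the planned Week 100 proportion, and is a reason to label the result, not to omit it.

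**Conclusion.** The point holds as a gap in estimation. Durability is a stated aim, PASI is collected every 6 weeks, and no endpoint or method turns those data into a duration. The certain part is the visit count: relapse after Week 52 is resolved to 48 weeks by the named timepoints and to 6 weeks by the data.

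The power gain is secondary and depends on assumptions: about 50% against 31% with everyone clear at Week 28, and about 32% against 21% with 80% clear, for medians of 24 and 72 weeks. Setting the log-rank against a single landmark (24% at Week 100, 12% at Week 52) would suggest a larger advantage, but the plan tests four landmarks without adjustment, so the four together are the fair comparator.

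A reader might also infer that a time-to-event analysis would make the durability comparison adequately powered. It would not: about 14 events are expected in that scenario against about 26 needed, and the interval for the restricted mean difference spans roughly 0 to 43 weeks. The change is worth making because it is cheap and supplies an estimate the plan lacks.

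**What to change.** Add one descriptive endpoint to Section 3 and its method to Section 9.7.

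- **Population:** all FAS patients as randomised. Do not start the clock at first PASI 100: only patients who clear could enter, which conditions on a post-randomisation outcome and breaks the randomised comparison.
- **Endpoint:** time from a fixed origin, for example Week 28, to the first visit without PASI 100, through Week 100, and likewise for PASI 90. Patients not clear at the origin count as events at time zero. Weeks spent clear, or restricted mean time clear, is an acceptable alternative.
- **Exits:** count study exit for lack of efficacy or intolerance as loss, in line with the composite strategy in Section 9.4; censor other exits.
- **Transient loss:** state whether a single non-clear visit that later clears counts as loss.
- **Reporting:** Kaplan-Meier curves by arm, medians or restricted mean difference with 95% CI, and a permutation log-rank p-value marked exploratory. Label timing after Week 52 as unblinded. Keep the landmark proportions.

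The cost is protocol and SAP wording, one table and one figure, with no new visits or data. The downside is wide intervals and open-label relapse timing in the last 48 weeks.

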4.3. JUSTIFICATION FOR DOSE

Risankizumab, an anti-IL-23 biologic, is highly effective and safe for treating plaque psoriasis.⁹⁻¹¹ The standard dose for this drug is 150 mg at Weeks 0 and 4, and then 150 mg every 12 weeks after two induction doses. Approximately 80% of patients reach PASI 90 and approximately 60% reach PASI 100 at 1 year, with few-to-no side effects.⁹⁻¹¹ In addition, the IMMhance study revealed that some patients undergoing risankizumab withdrawal demonstrated prolonged skin clearance long after their last dose.¹¹

When testing higher doses of risankizumab (600 mg or 300 mg at Weeks 0, 4, and 16), as described here, it is possible that efficacy will be higher than reported with standard dosing. It is also possible that disease remission following drug withdrawal will be longer than remission reported following drug withdrawal after standard dosing of risankizumab.

Indeed, doses of risankizumab higher than standard dosing used for psoriasis have been used to treat other diseases, such as Crohn's disease. No new or different side effects were seen with higher doses of risankizumab in these studies. Thus, the side effect profile in the current proposed study is expected to be favorable.

4.4. END OF STUDY DEFINITION

Patients will be observed for 100 weeks after their first dose of risankizumab (84 weeks after their last dose of risankizumab).

5. STUDY POPULATION

5.1. INCLUSION CRITERIA

1. Subject has provided written consent
2. Subject has the ability to comply with all study visits and procedures
3. Subject is at least 18 years of age
4. Subject has chronic stable plaque psoriasis:
 - a. For at least 6 months
 - b. Severity of BSA ≥ 10 and PASI ≥ 12
5. Female subjects of child-bearing potential must have a negative urine test at screening and baseline. Female subjects must be either postmenopausal, or permanently surgically sterile, or for women of child-bearing potential practicing at least one form of birth control (Section 5.6)

5.2. EXCLUSION CRITERIA

1. Breastfeeding or pregnant women, or women who plan to become pregnant during study period
2. Participation in any other clinical trial
3. Active infection with HIV, hepatitis B virus, or hepatitis C virus
4. Active infection with tuberculosis or untreated latent tuberculosis
5. History of known active cancer, other than non-melanoma skin cancer or cervical carcinoma *in situ*, in the past 3 years
6. History of drug or alcohol abuse in the past 6 months, as per investigator's assessment
7. History of suicidal ideation or attempts in the past 6 months
8. Presence of any concurrent illness, which in the opinion of the investigator, would place the patient at unnecessary safety risk during the trial or interfere with completion of the trial
9. Treatment with topical medications for psoriasis in the past 2 weeks
10. Treatment with oral medications for psoriasis in the past 4 weeks
11. Phototherapy for psoriasis in the past 4 weeks
12. Any prior treatment with risankizumab

13. Treatment with biologic medications for psoriasis (other than risankizumab) in the past 4 months

5.3. LIFESTYLE CONSIDERATIONS

None.

5.4. SCREEN FAILURES

Screen failures are defined as participants who consent to participate in the clinical trial but are not subsequently randomly assigned to the study intervention or entered in the study. A minimal set of screen failure information is required to ensure transparent reporting of screen failure participants, to meet the Consolidated Standards of Reporting Trials (CONSORT) publishing requirements and to respond to queries from regulatory authorities. Minimal information includes demography, screen failure details, eligibility criteria, and any serious adverse event (SAE). Individuals who do not meet the criteria for participation in this trial (screen failure) may not be rescreened. Laboratory assessments used to determine subject eligibility may be repeated during the screening period before the subject is considered a screen failure.

5.5. STRATEGIES FOR RECRUITMENT AND RETENTION

OMRC, the sponsor of this trial, has a large database of psoriasis patients. We will recruit patients from this database as well as from general Google ads and referrals from community dermatologists.

5.6. CONTRACEPTION RECOMMENDATIONS

Female subjects of child-bearing potential must be ready and able to use highly effective methods of birth control, or subjects must have only vasectomized sexual partner(s) or be abstinent throughout the study. Women of child-bearing potential are defined as: having experienced menarche, and are not postmenopausal (12 months with no menses without alternative medical cause), and are not permanently sterilized (e.g., tubal occlusion, hysterectomy, bilateral oophorectomy, or bilateral salpingectomy).

The following is a list of accepted contraception methods:

- Combined (estrogen and progesterone containing) hormonal contraception (oral, intravaginal, transdermal, injectable) associated with the inhibition of ovulation, initiated at least 1 month prior to study
- Progestogen-only hormonal contraception (oral, injectable, implantable) associated with the inhibition of ovulation, initiated at least 1 month prior to study
- Bilateral tubal occlusion/ligation
- Vasectomized partner(s)
- Intrauterine device (IUD) or intrauterine hormone-releasing system (IUS)
- True abstinence (refraining from heterosexual intercourse when this is in line with the preferred and usual lifestyle of the subject). Periodic abstinence (e.g., calendar, ovulation, symptothermal, post-ovulation methods) and withdrawal are not acceptable.

6. STUDY INTERVENTION

6.1. STUDY INTERVENTION(S) ADMINISTRATION

6.1.1. STUDY INTERVENTION DESCRIPTION

The IB for risankizumab (Skyrizi®), approved by the FDA for use in patients with moderate-to-severe psoriasis, is included with the IRB submission.

6.1.2. DOSING AND ADMINISTRATION

Twenty patients with moderate to severe plaque psoriasis will be randomized in a 1:1 manner to receive either risankizumab 600 mg (4X dosing) or 300 mg (2X dosing), SC, at Weeks 0, 4, and 16. All patients will receive four SC injections at Weeks 0, 4, and 16 (into right arm, left arm, right thigh, left thigh) by an unblinded pharmacist. For patients randomized into the highest induction dose arm, each shot will contain 150 mg of risankizumab; for patients randomized into the 2X induction dose arm, two shots will contain 150 mg of risankizumab each and 2 shots will contain placebo (sterile saline).

